In a pre-clinical study,⁹ we investigated UA as an agent affecting anabolic, metabolically-linked signaling pathways in muscle, and explored phenotypic outcomes in sublesional muscle following traumatic SCI. Our primary objectives were to examine following experimental SCI i. intracellular mTOR signaling, ii. The expression of related catabolic genes, and iii. The effects on these outcomes with UA treatment. We hypothesize that SCI would i. reduce growth pathways via mTOR signaling, ii. Increase the expression of catabolic genes, and iii. UA will attenuate these SCI-induced changes. In addition, we examined the effect of SCI on physical and functional measures, and whether UA-promoted signaling in muscle translated to improvements in these outcome measures. When examining effects of UA treatment on sublesional muscle mTOR signaling, catabolic genes, and functional deficits following severe SCI in mice we observed that UA treatment significantly attenuated SCI-induced decreases in activated forms of mTOR, and signaling intermediates PI3K, AKT, and S6K, and the upregulation of catabolic genes including FOXO1, MAFbx, MURF-1, and PSMD11. In addition, UA treatment improved SCI-induced deficits in body and sublesional muscle mass, as well as functional outcomes related to muscle function, motor coordination, and strength.

These findings provided first evidence that UA treatment may be a potential therapeutic strategy to improve muscle specific pathological consequences of SCI.

6. Inclusion and Exclusion Criteria

Inclusion Criteria

- 18-65 years of age
- Aim 1: Male and female individuals with paraplegia having chronic (≥ 1 year) complete and incomplete (AIS A/B/C) injuries from T2-T8
- Aim 2: Male and female individuals wi4.th chronic (≥ 1 year) complete and incomplete (AIS A/B/C) injuries from C4-C7

Exclusion Criteria

- Pregnant or planning to become pregnant
- Women who are breastfeeding

Number of Subjects

- Aim 1 will enroll up to 10 participants
- Aim 2 will enroll up to 10 participants

7. Study Recruitment Methods

Recruitment will include IRB-approved flyers posted throughout the Christine E. Lynn Rehabilitation Center for the Miami Project to Cure Paralysis; social media; word-of-mouth at the Christine E. Lynn Rehabilitation Center for the Miami Project to Cure Paralysis; online advertisement using IRB-approved language from flyers, telephone or email contact for those individuals who have previously consented for contact in other studies.

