The co-primary outcomes will be lean mass and peak strength.

- Aim 2 subjects will:
 - Subjects will receive 2 bottles of oral UA every month
 - Subjects will be asked to take 400 mg or 8 capsules (4 in the morning/200mg and 4 at night/ 200mg) daily for 12-weeks.
 - Adherence to the UA intervention will be done once a month by study staff and will entail:
 - collection of used bottle
 - counting remaining capsules, if any
 - calculation of compliance: [(days x 8) capsules remaining]
 - and dispensing a new bottles.

**Education regarding the importance of compliance to the dosing requirements will be part of the monthly drug accountability.

*** Research Studies Subjects will be offered participation in other PM&R and Miami Project to Cure Paralysis studies for which they may be eligible. The possibility of dual enrollment or partial overlap of participation in more than one study is conceivable. This could result in duplication of required assessments subjects would need to complete. However, to simplify participation, reduce the number of visits to our research lab, and mitigate testing redundancy, we may apply test results completed for one study to another in those cases.

- Whole body lean mass will be determined by DXA and CT scan before and after 12 weeks of treatment.
- Before and after the 12-week UA intervention an oral glucose tolerance test (OGTT: 75 g glucose as TrutolTM) will be administrated following an overnight fast.
 - Bloods taken before glucose ingestion will be analyzed for glucose, insulin, and inflammatory biomarkers (TNF-alpha, IL-6, and CRP).
 - Bloods will also be taken at 30-minute intervals for two hours.
- Maximal inspiratory pressure will be measured with the Pro2 Fit device.

Co-primary outcomes will be the fasting IR determined by the HOMA v2 model and the rates of glucose disposal defined by the area under the glucose challenge curve (AUC).

Dual X-ray Absorptiometry (DXA)*

The regional composition for Fat Free Mass (FFM), Fat Mass (FM), % FM, and Lean Mass (LM), in regions of interest including the trunk, arms, android, and gynoid regions will be measured by DXA as described by Gorgey et al., Spinal Cord 2018. Body composition will be measured by whole body scans using a GE

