Subjects refraining from alcohol and caffeine ingestion starting 24 hours before testing will be studied in the postabsorptive state after a 10-hour overnight fast. Under antiseptic conditions, a 21-gauge Teflon catheter (Jelco) with multi-sample Luer connector will be inserted in a superficial arm vein by a State of Florida Certified Phlebotomist. The catheter is kept patent with sterile physiological (0.9%) saline. Blood samples obtained at rest and during the OGTT (taken at 30-minute intervals for two hours) will be collected in NaF (glycolysis), clot lysis activator (serum), and citrated Vacutainer tubes, and then centrifuged at 8,000g for 30 minutes to isolate the serum. These isolates will be tested on a Roche Mira-Cobas Automated Chemistry Analyzer (Roche Diagnostic Systems, Basel, Switzerland), as we have described.

Oral Glucose Tolerance Test (OGTT)

Baseline blood sample will be drawn (see to blood analyte for procedure details) after an overnight fast. Subjects will them be given Trutol glucose solution that contains seventy five (75) grams of glucose, similar in taste to a very sweet soda (usually orange flavor). Subjects will be instructed to complete ingestion within five (5) minutes.

After drinking the Trutol, blood will be drawn at exactly 30 minute intervals for two hours. Blood collection process is detailed in the Blood Analyte Testing section.

Subjects must refrain from eating/drinking anything other than water for the duration of the test, approximately 2.5 hours.

Insulin Resistance

Insulin resistance will be computed using the Homeostatic Model of Mathews (HOMA; computer version v.2:

[https://www.dtu.ox.ac.uk/homacalculator/download.php]) Criterion scores for normal, glucose intolerant, and insulin resistant were published by Nash, et al., Arch Phys Med Rehabil, 2016.

Strength

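### Optional improvement: the Aim 2 co-primary HOMA2 appears to rest on one fasting sample per visit, and averaging three draws through the catheter already in place would cost little and raise precision

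*Combined protocol and SAP*

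**What the plan says.** Section 9, under Aim 2, defines the endpoint: "Co-primary outcomes will be the fasting IR determined by the HOMA v2 model and the rates of glucose disposal", the latter taken from the area under the glucose curve. Section 11 (Data analysis) repeats the pair and applies a Bonferroni correction with α = 0.05.

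Three places bear on how many fasting draws feed HOMA2:

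- Section 9, Oral Glucose Tolerance Test, uses the singular: "Baseline blood sample will be drawn (see to blood analyte for procedure details) after an overnight fast". Draws every 30 minutes for two hours follow the glucose drink.
- Section 9, Aim 2, uses a plural without a number: "Bloods taken before glucose ingestion will be analyzed for glucose, insulin, and inflammatory biomarkers (TNF-alpha, IL-6, and CRP").
- Section 9, Insulin Resistance, names the calculator but not its inputs: "Insulin resistance will be computed using the Homeostatic Model of Mathews (HOMA; computer version v.2").

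The means of taking more samples is already described. Under Blood Analyte Testing, "a 21-gauge Teflon catheter (Jelco) with multi-sample Luer connector will be inserted in a superficial arm vein", and "The catheter is kept patent with sterile physiological (0.9%) saline".

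On size, Section 6 says "Aim 2 will enroll up to 10 participants". Section 11 needs no randomization for this aim, so it is a single group measured before and after 12 weeks. No effect size, SD or power is stated.

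**The concern.** Suppose each visit's HOMA2 comes from one fasting draw, and that fasting glucose and insulin carry some draw-to-draw and assay noise. That noise then enters the change score twice, once at each visit. With at most 10 participants the change is estimated imprecisely to begin with, and noise that could be averaged away inside an existing visit is worth removing. By comparison, the exploratory inspiratory pressure test in Section 9 (Strength) allows up to 6 maneuvers, while no repeat is described for the fasting sample behind a co-primary. Section 10 says that no residual specimens are banked, so a noisy fasting value cannot be re-assayed later, and a baseline already taken with one draw cannot be improved.

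**Working it through.** The plan gives no power or variance figure, so there is nothing to reproduce. The calculation shows how much averaging could matter.

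**Inputs from the documents:** n = 10 (the Section 6 maximum); two visits; α = 0.05 with Bonferroni over two co-primaries, read as 0.05/2 = 0.025 each.

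**Assumptions, not in the documents:** two-sided testing; paired t-test on the change in log HOMA2; a true 25% fall, so an effect of |ln 0.75| = 0.2877; visit-to-visit SD s_b of 0.15 to 0.25 and within-visit single-draw SD s_w of 0.10 to 0.30, both on the log scale; independent within-visit errors; the same response in everyone.

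**Formula:** with k draws averaged at each visit, SD of change = √[2(s_b² + s_w²/k)]. Power comes from the noncentral t with 9 degrees of freedom, noncentrality 0.2877·√10/SD and critical value 2.685.

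**Midpoint (s_b = 0.20, s_w = 0.20):**

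- k = 1: SD = √[2(0.04 + 0.04)] = 0.400; standardized change 0.719; power 39%.
- k = 3: SD = √[2(0.04 + 0.0133)] = 0.327; standardized change 0.881; power 56%.

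**Whole grid, power with one draw → three draws:**

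| s_b | s_w = 0.10 | s_w = 0.20 | s_w = 0.30 |
|---|---|---|---|
| 0.15 | 79% → 88% | 49% → 75% | 28% → 57% |
| 0.20 | 59% → 66% | 39% → 56% | 24% → 44% |
| 0.25 | 43% → 47% | 31% → 41% | 21% → 34% |

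Power rises in all nine cells. The smallest gain is 42.8% to 46.7% (about 4 points) and the largest is 27.9% to 56.8% (about 29 points).

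**Relaxing the assumptions at the midpoint:**

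- Within-visit errors correlated at 0.6: the within-visit term becomes 0.04 × (1 + 2 × 0.6)/3 = 0.0293, the SD with three draws is √[2(0.04 + 0.0293)] = 0.372, and power goes from 39% to 45%.
- Response varying between people with SD 0.20: this adds 0.04 to both variances, so the SDs are √0.20 = 0.447 and √0.1467 = 0.383, and power goes from 31% to 42%.
- No within-visit noise (s_w = 0): the two SDs are equal and there is no gain.
- α = 0.05 instead of 0.025: 53% to 70%, so the direction does not depend on how the Bonferroni rule is read.

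**The case against.** The strongest reply is that nothing here is broken. The study is a pilot with no power target, no passage contradicts another, and an analysis of single draws would be valid, only less precise. That stands, and it is why the point is offered as optional. A reader might infer that the plan contains an error or that the HOMA2 result would be unsound; the documents support neither.

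A second reply is that the single draw is inferred. The OGTT text is singular, but the Aim 2 text is plural, and Blood Analyte Testing also speaks of samples at rest in the plural. Those plurals fit several tubes or analytes, so one draw is the likelier reading, but it is not stated outright. If replicates are intended, the protocol still does not give their number, spacing or averaging rule.

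A third reply is that the size rests on assumption. That also stands. The protocol reports no within-visit or assay variance. Draws 5 minutes apart, perhaps assayed together, may share error, and people may differ in response; both reduce the gain, as shown above.

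A reader might also infer that within-visit noise is the only variance the sponsor can reduce without enrolling more people. That goes too far. A repeat baseline visit or tighter pre-test standardization could reduce visit-to-visit variation, which averaging within a visit leaves untouched. Replicate draws are simply an option that fits inside the visits already planned.

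**Conclusion.** The point holds as a low-cost, optional improvement. As written, HOMA2 appears to rest on one fasting sample per visit, with no replicate or averaging rule, although the line for further draws is in place. Averaging three draws raises power whenever within-visit errors are not perfectly shared. The size is uncertain: 39% to 56% at the midpoint under favourable assumptions, 39% to 45% with correlated errors, 31% to 42% with varying response, and nothing if there is no within-visit noise. These figures illustrate the direction and possible scale and should not be quoted as estimates for this trial.

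Nor should the change be read as rescuing Aim 2. At the midpoint, power is still only 56% afterwards, and better precision does not supply the control group needed to attribute a change to ursolic acid.

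**What to change.** In Section 9, under Oral Glucose Tolerance Test and Insulin Resistance, add text such as: *At both the baseline and the 12-week visit, three fasting samples are drawn through the catheter about 5 minutes apart before Trutol. Glucose and insulin are each averaged, HOMA2 is computed from the means, and the mean fasting glucose is the time-zero point of the AUC.* Align the Aim 2 text of the same section so that the number of fasting draws reads the same throughout. The rule should be in place before the first baseline visit, so that both visits are measured alike.

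The cost is 10 participants × 2 visits × 2 extra draws = 40 additional paired glucose and insulin assays, slightly more blood, and about 10 minutes per visit. It needs no extra visit, staff or venepuncture. If the sponsor prefers one draw, a sentence saying so would remove the ambiguity at no cost.

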UA will be sourced as Biotech Nutritions Ursolic Acid Gelatin Free Non-GMO capsules (i.e. form) ; 200mg (4 total capsules, 50mg each) taken twice daily by mouth with food and a non-alcohol-containing drink. UA is a non-Rx nutraceutical obtained without prescription. We will neither claim an FDA 'brand' for the product, nor propose a new or extended indication for its use.

Manufacturer: Biotech Nutritions [name] Ph: [name]

- Aim 1: will couple UA administration at doses that increase muscle mass with strengthening exercise performed in one arm only.
 - Subjects will receive 2 bottles of oral UA every month. Subjects will be asked to take 400 mg or 8 capsules (4 in the morning/200mg and 4 at night/ 200mg) daily for 12-weeks
 - Adherence to the UA intervention will be done once a month by study staff and will entail:
 - collection of used bottle(s)
 - counting remaining capsules, if any
 - calculation of compliance: [(days x 8) capsules remaining
 - and dispensing a new bottle(s).

**Education regarding the importance of compliance to the dosing requirements will be part of the monthly drug accountability.

*** Research Studies Subjects will be offered participation in other PM&R and Miami Project to Cure Paralysis studies for which they may be eligible. The possibility of dual enrollment or partial overlap of participation in more than one study is conceivable. This could result in duplication of required assessments subjects would need to complete. However, to simplify participation, reduce the number of visits to our research lab, and mitigate testing redundancy, we may apply test results completed for one study to another in those cases.

- During this period, one upper limb (only), randomized by selection, will undergo exercise conditioning three times weekly using a strengthening program we have established to increase muscle mass and strength in people with SCI. The other arm will remain untrained as a control receiving the same whole body dose of UA.
- Lean mass will be examined before and after 12 weeks of treatment using dual-ray absorptiometry (DXA) and non-contrast CT scan of both arms, with the area of interest identified from the glenohumeral joint distally to the ulnar styloid.
- Peak isokinetic strength of both arms at 90 degrees of flexion will be tested in elbow flexion and extension on a Biodex dynamometer.
- Maximal inspiratory pressure will be measured with the Pro2 Fit device.

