- Data for the trial will be managed using a secure data repository system database (box or redcap), and through paper and pencil. Regulatory trial management may use the Complion INC e-regulatory system platform. All data collected will be entered into a secured data collection system. All participating centers in this multi-site project will have access to the coded deidentified data collected as a part of the study.

11. Data Management

Randomization

- For Aim 1, the dominant or non-dominant arm assigned to resistance exercise (versus non-exercise) will be randomized in equal numbers using the 'RAND' function in Microsoft Excel.
- No randomization is required for Aim 2.

Data analysis

- Will be performed using a repeated measures design corrected for multiple comparisons (Bonferroni) with co-primary outcomes for Aim 1 of *mass* and *strength*, and Aim 2 for co-primary outcomes of *IR* and *glucose disposal*. Other outcomes will be considered exploratory.
- Non-parametric techniques will be used, or data transformed, if the data fail a test of normality or homogeneity of variance. $\alpha = 0.05$ for all testing will represent the threshold value used to judge whether a test statistic is significant.

12. Confidentiality and Subject's Data Safety

• Physical/paper records will be stored in a locked room at the Miami Project (Christine E. Lynn Rehabilitation Center, [name]) in a lockable file cabinet only accessible to study personnel in the. A security badge is needed to open the office door where data are stored. Access to Miami Project (Lynn Center 2nd Floor) is via a universityissued hallway proximity card after passing a security guard located in the front lobby.

- There are two types of electronic records, 1) source data and 2) pdf versions of all paper and electronic data.
 - Source electronic data will be stored in the original collection location. In addition, a copy of the electronic file may be stored on the Miami Project Server in a working group with restricted access. The Miami Project server is behind UM firewalls and is backed up electronically daily, with tapes of older copies archived off site in a fire/hurricane secure facility.
 - All electronic and paper source data will also be stored electronically as pdf's in an electronic version of the participant's folder. Paper source data will be scanned, and electronic source data will be saved as a pdf.
- Data Storage Duration

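### Holm's step-down could replace Bonferroni for the two co-primaries in each aim: same family-wise error, never fewer rejections, more power for the second outcome only

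*Combined protocol and SAP*

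**What the plan says.** Section 11 (Data analysis) specifies a "repeated measures design corrected for multiple comparisons (Bonferroni) with co-primary outcomes for Aim 1", these being mass and strength, and for Aim 2 insulin resistance and glucose disposal. All other outcomes are exploratory. The next bullet sets alpha at 0.05 for all testing and gives no adjusted per-test level.

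Section 9 names the same pairs. For Aim 1: "The co-primary outcomes will be lean mass and peak strength". For Aim 2: "Co-primary outcomes will be the fasting IR determined by the HOMA v2 model and the rates of glucose disposal", the latter defined by the area under the glucose curve.

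Section 6 limits the numbers: "Aim 1 will enroll up to 10 participants" and "Aim 2 will enroll up to 10 participants". No power target, effect size or standard deviation is given, and no stepwise procedure is mentioned.

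**The concern.** With two outcomes, plain Bonferroni at family-wise 0.05 tests each at 0.025. A second co-primary with p between 0.025 and 0.05 is then non-significant even when the first has already passed. Holm's step-down would accept it at the same family-wise error. With at most 10 participants per aim there is little information to spare, and the protocol does commit to significance testing. The choice must also be made beforehand: moving to Holm after seeing a second p-value of, say, 0.03 would not be credible.

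**Working it through.** **Inputs from the documents.** Two co-primaries per aim (Sections 9 and 11); Bonferroni and alpha 0.05 (Section 11); at most 10 participants per aim (Section 6).

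**Assumed.** The family is the two co-primaries; tests are two-sided paired t tests on one change per participant and outcome; changes are bivariate normal; true effects are 0.5, 0.8 or 1.0 SD of the change; correlation between outcomes is 0.3 to 0.6. The plan has no power figure of its own to reproduce.

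**Step 1: the two rules.**
- Bonferroni: reject each outcome with p ≤ 0.05/2 = 0.025. Family-wise error is at most 0.025 + 0.025 = 0.05.
- Holm: test the smaller p against 0.025; if it passes, test the other against 0.05.

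The first step is the same, so Holm rejects everything Bonferroni rejects. The decisions differ only when one p is at most 0.025 and the other lies between 0.025 and 0.05.

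**Step 2: error control.** If both nulls are true, any rejection needs the smaller p to be at most 0.025, so the two methods have identical family-wise error (simulated 4.6% for both at correlation 0.5). If one null is true, a false rejection needs that outcome's own p to be at most 0.05, so Holm's error is again at most 0.05. With effects of 0.8 SD and zero at correlation 0.5, the null outcome is rejected in 2.5% of trials under Bonferroni and 3.8% under Holm. Neither argument uses the correlation.

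**Step 3: power of one test at 0.025.** Power = P(|T| > t(0.9875; 9 df)), where T is noncentral t with 9 df and noncentrality d√10. This gives 19.2%, 47.5% and 68.2% for d = 0.5, 0.8 and 1.0, which checks the simulation.

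**Step 4: both methods compared.** Simulation, 200,000 replicates, n = 10, equal effects, correlation 0.5:

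| True effect | Per outcome, Bonferroni → Holm | Both significant, Bonferroni → Holm | At least one, either method |
|---|---|---|---|
| 0.5 SD | 19.1% → 21.8% | 7.3% → 12.8% | 30.8% |
| 0.8 SD | 47.5% → 54.0% | 29.6% → 42.6% | 65.4% |
| 1.0 SD | 68.1% → 75.3% | 52.3% → 66.6% | 83.9% |

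Consistency check at 0.8 SD, using P(at least one) = sum of the two powers minus P(both): Bonferroni 47.5 + 47.5 − 29.6 = 65.4; Holm 54.0 + 54.0 − 42.6 = 65.4. The gain in both-significant (13.0 points) is twice the gain per outcome (6.5 points), as it must be when the effects are equal.

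Across correlations 0.3 to 0.6, both-significant rises from 26–31% to 40–44% at 0.8 SD and from 50–54% to 65–68% at 1.0 SD.

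**Step 5: only one real effect.** With 0.8 SD on one outcome and none on the other, correlation 0.5, power for the real effect is 47.6% under Bonferroni and 47.8% under Holm.

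**The case against.** Bonferroni is valid and prespecified, and no stated power is missed, so preferring Holm could be called taste. That stands in so far as the plan contains no error here. It does not remove the case for a rule that never rejects less at the same error level.

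A reader might infer that the plan gives up power for nothing, or that Holm makes a positive finding more likely overall. The documents and the arithmetic do not support either. The chance of at least one significant co-primary is the same. The gain is modest for moderate effects. Bonferroni also has simple 97.5% intervals that agree with its tests, which matters in a pilot whose Aim 1 is to explore effects.

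A reader might also infer that any second p-value between 0.025 and 0.05 will certainly be called non-significant. That needs a per-test level of 0.025, which the plan never states. Section 11 does not say whether the correction covers the co-primaries, the repeated-measures contrasts (arm by time in Aim 1), or both. Nor is the number of tests fixed: strength "will be tested in elbow flexion and extension on a Biodex dynamometer", and lean mass uses "dual-ray absorptiometry (DXA) and non-contrast CT scan of both arms". This objection stands. Two tests per aim is the natural reading because the same sentence lists the outcomes, but the fix has to define the family and must not drop a correction meant for other contrasts.

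Finally, if co-primary meant that both outcomes must succeed, each could be tested at 0.05 without adjustment and neither method would be needed. Planning a Bonferroni correction points away from that reading, but the protocol should say so.

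**Conclusion.** A worthwhile improvement at almost no cost, not the correction of an error. Under the assumptions listed, Holm adds about 3 points of power per outcome at 0.5 SD (19% to 22%), 6 to 7 at 0.8 SD and 7 to 8 at 1.0 SD, with larger gains in the chance that both are significant. All of the benefit falls on the second co-primary after the first has passed, and it is about nil if only one effect is real.

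That Holm has the same error control and never rejects less does not depend on the assumed effects or correlation. The size of the gain does, and the documents support no particular values. It also rests on two tests per aim and 10 analysed participants. Section 13 withdraws participants below 80% adherence, so the analysed number may be smaller.

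**What to change.** In Section 11 (Data analysis), state that:
- within each aim, one prespecified test per co-primary forms the family: one mass measure and one strength measure for Aim 1, HOMA2 insulin resistance and glucose AUC for Aim 2;
- the family is tested by Holm's procedure at family-wise 0.05: the smaller p against 0.025 and, if significant, the other against 0.05;
- either outcome alone supports a claim about that outcome;
- any Bonferroni correction intended for further repeated-measures contrasts is kept, with those contrasts listed.

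The cost is one or two sentences before the data are seen; no extra participants or measurements are needed. The one drawback is in the intervals. Reporting 97.5% intervals keeps valid simultaneous coverage, but such an interval can include zero for an outcome that Holm declares significant with p between 0.025 and 0.05. The report should note this where it happens.
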